### **Statistical Analysis**

Quantitative values will be expressed as mean  $\pm$  standard deviation, median and range; categorical data with percentage frequencies. Mean values of duration of stay will be compared according to the presence or absence of fistulas using Student's two-sided t test (allowing for heterogeneity of variances) or with a non-parametric Mann-Whitney test. Mean values of DULK score, CRP and PCT levels will also be compared using Student's two-sided t test (allowing for heterogeneity of variances) or with a non-parametric Mann-Whitney test. Both univariate analysis and multivariate analysis will be performed to assess risk factors for leakage and overall complications. The odds ratio (OR) will be presented followed by its 95% confidence interval (95% CI). Areas under the receiver-operating characteristics (ROC) curve will be calculated. For all statistical tests the significant level is fixed at  $p < .05$ . Multivariate analysis will be performed using logistic models.

Statistical analyses will be carried out using STATA software (Stata Corp. College Station, Texas, USA).

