## **METHODS**

Prospective enrollment from September 2017 to November 2018 in 20 Italian surgical centers. All patients undergoing elective colorectal surgery with anastomosis will be included in a prospective database after having provided a written informed consent. A total of more than 1,160 patients is expected based on a mean of 50 cases/year per center.

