#### **Recorded data and follow-up**

Potential patient-specific and intraoperative risk factors will be recorded: gender, body mass index, nutritional status according to the Mini Nutritional Assessment short-form [17, 18], surgical indication (cancer, polyps, chronic inflammatory bowel disease, diverticular disease), preoperative albuminemia, use of steroids, renal failure and dialysis, preoperative leukocyte count, CRP, PCT cardiovascular or respiratory disease, American Society of Anesthesia score, bowel preparation (decision made by operating surgeon), laparoscopy or laparotomy, level of anastomosis and technique (mechanical or hand-sewn, intra- or extra-corporeal), operative time, presence of drainage, surgeon and perioperative blood transfusion(s). During the postoperative period, patients will be examined by the attending surgeon daily. Fever (central temperature > 38 °C), pulse, abdominal signs, bowel movements, volume and aspect of drainage (if present) will be recorded daily. Leucocyte count, CRP, PCT and Dulk score will be measured in the evening before the operation (in addition to albuminemia) and on postoperative days 2, 3, and 6 (optional). The attending surgeon will make any decision for complementary exams and imaging according to his own criteria. The rate of any complication will be calculated and graded according to Clavien-ALL 3 – Protocollo dello Studio

Dindo [15, 16] including all leaks (independently of clinical significance), wound infection, pneumonia, central line infection, urinary tract infection. Urinary tract infection will be diagnosed on the basis of positive urine culture with bacterial count. Central line infection will be diagnosed on the basis of positive blood culture. Superficial and deep incisional infections will be diagnosed according to the definitions of the Centers for Disease Control and Prevention and a culture will be performed [19]. Pneumonia will be diagnosed on the basis of clinical symptoms, and physical and radiological examinations. The surgeons will be blinded to the results of the CRP and PCT assays. Patients will be followed-up in the outpatient clinic up to 6 weeks after discharge from the hospital.

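### The risk-factor logistic models make no provision for the 20 centres, so intervals and p-values for practice-related factors are too optimistic if event or detection rates differ between centres

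*Protocol*

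**What the plan says.** Protocol, METHODS, describes the setting: "Prospective enrollment from September 2017 to November 2018 in 20 Italian surgical centers". It adds: "A total of more than 1,160 patients is expected based on a mean of 50 cases/year per center".

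Protocol, Statistical Analysis, sets out the risk-factor analysis: "Both univariate analysis and multivariate analysis will be performed to assess risk factors for leakage and overall complications". The model is named in one line: "Multivariate analysis will be performed using logistic models". Reporting is also fixed: "The odds ratio (OR) will be presented followed by its 95% confidence interval (95% CI"), and "For all statistical tests the significant level is fixed at" p < .05. The section does not mention centre, surgeon, random effects or clustered standard errors. The Sample size section makes no allowance for clustering.

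Protocol, Recorded data and follow-up, lists the candidate factors. One is expressly a surgeon's choice: "bowel preparation (decision made by operating surgeon"). Laparoscopy or laparotomy is listed too, as is "technique (mechanical or hand-sewn, intra- or extra-corporeal), operative time, presence of drainage, surgeon and perioperative blood transfusion(s"). The same section leaves further tests and imaging to the attending surgeon. The main-outcome definition leaves postoperative CT to that surgeon's discretion, excludes routine imaging for leaks, and counts every detected leak whatever its clinical significance.

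**The concern.** A plain logistic model estimates standard errors as if, given the covariates, patients were independent. Two features of this design work against that.

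- **Exposure.** Bowel preparation, and plausibly drainage, anastomotic technique and approach, follow the habits of a surgeon or unit. Patients at one centre then tend to share the same exposure.
- **Outcome.** Leak rates may differ between centres. Even if true rates do not, detected rates can, because the decision to image rests with the surgeon and every detected leak counts.

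When exposure and outcome both cluster by centre, the information about the exposure comes largely from comparing 20 centres, not more than 1,000 patients. The plain model overstates that information. Its intervals are then too narrow and null factors reach p < .05 too often. The Background lists drains, bowel preparation and laparoscopic procedure among the controversial or inconclusive associations, and the study aims to settle what the risk factors are. The factors most exposed to this error are therefore among those it hopes to resolve.

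**Working it through.** **Cluster size.** 20 centres x 50 cases/year x 14/12 years = 1,167, which agrees with the expected total of more than 1,160. That is 1,160/20 = 58 per centre. At the required sample size, 1,062/20 = 53.1. I use m = 53.

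**Event rates.** The Background gives 2 to 7% for leakage, i.e. 0.02 x 1,062 = 21 to 0.07 x 1,062 = 74 leaks. I take 2% and 5%. The Protocol gives no rate for overall complications, so 25% is assumed.

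**Between-centre variation.** The Protocol gives none. I assume an SD of log-odds (s) of 0.3, 0.5 and 0.7.

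**Approximation.** On the proportion scale, ICC ≈ p(1-p)s². The design effect for a factor is DE = 1 + (m-1) x ICC x ICCx, where ICCx is the share of the exposure's variance that lies between centres (1 if fixed within centre, 0 for a factor unrelated to centre). The actual error of a nominal two-sided 5% test is 2[1 - Φ(1.96/√DE)].

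Example, p = 5%, s = 0.5, ICCx = 1: ICC = 0.05 x 0.95 x 0.25 = 0.0119; DE = 1 + 52 x 0.0119 = 1.62; 1.96/√1.62 = 1.54; error = 12%.

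**Null factor fixed within centre.** Simulated values are for a plain logistic model with 20 x 53 patients and a random centre intercept.

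| Event rate | s | ICC | DE | Error, formula | Error, simulated |
|---|---|---|---|---|---|
| 2% | 0.3 | 0.0018 | 1.09 | 6% | 6% |
| 2% | 0.5 | 0.0049 | 1.25 | 8% | 7% |
| 2% | 0.7 | 0.0096 | 1.50 | 11% | 11% |
| 5% | 0.3 | 0.0043 | 1.22 | 8% | 6% |
| 5% | 0.5 | 0.0119 | 1.62 | 12% | 10% |
| 5% | 0.7 | 0.0233 | 2.21 | 19% | 20% |
| 25% | 0.3 | 0.0169 | 1.88 | 15% | 14% |
| 25% | 0.5 | 0.0469 | 3.44 | 29% | 28% |
| 25% | 0.7 | 0.0919 | 5.78 | 41% | 39% |

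Formula and simulation agree to within about two percentage points. A correct interval is √DE times as wide as the plain one: √1.62 = 1.27 at 5% and s = 0.5, and √3.44 = 1.85 at 25% and s = 0.5.

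**Practice that varies within centres.** Suppose half the centres use a technique in 90% of patients and half in 10%. Then ICCx = 0.4²/0.25 = 0.64. Simulated error at leak rates of 4-7% is 6-7%, 10-12% and 14-20% for the three SDs. At a 2% leak rate it is about 5% and 6% for s = 0.3 and 0.5. With a 70%/30% split, ICCx = 0.2²/0.25 = 0.16, and error at leak rates of 4-7% is 4-6%, 6-8% and 7%. For overall complications at 25%, the 90%/10% split gives 10%, 21% and 30%.

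**Patient-level factor.** With ICCx = 0, DE = 1 and the error stays at 5%; simulation gives 4-6%.

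**After correction.** Cluster-robust standard errors with t critical values bring the error to about 5-7%. In one set of runs it reached 8% for leakage at the largest SD.

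**The case against.** The strongest reply is that the Protocol is merely silent. It never says that patients will be treated as independent, and a random-intercept or cluster-robust logistic model is still a logistic model. A statistical analysis plan that is not at hand might settle the matter. This stands in part: a reader might infer an explicit independence assumption, and the text contains none. But the section does fix the model family, the interval and the test level, and carrying it out as written gives the results above.

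Second, surgeon choice is documented only for bowel preparation. This also stands. A reader might infer that all technical factors are dictated by the centre, but drainage, technique and approach are only listed. Their link to local habit is plausible, not stated.

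Third, the effect may be small. At a 2% leak rate with modest heterogeneity, or when practice varies mostly within centres, the error for leakage stays near 5%. A general claim that the study will run well above its stated error rate is not supported.

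Fourth, the main comparisons are largely untouched. ASA class, on which the sample size rests, is a patient-level factor, as are sex and BMI. The calculations here do not bear on the diagnostic yield of the DULK score, CRP or procalcitonin.

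Finally, surgeon is a recorded variable. Recording it does not put it in the model, and the Protocol does not say how it would be used.

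**Conclusion.** The concern holds in a conditional form. If event or detection rates differ between centres, the logistic models as written give p-values and 95% intervals that are too optimistic for factors following surgeon or centre practice: bowel preparation on the Protocol's own statement, and plausibly drainage, technique and approach.

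For a factor fixed within centre, the type I error at a nominal 5% is about 6-11% at a 2% leak rate, 6-20% at 5%, and 14-39% for overall complications. These ranges rest on an assumed SD of 0.3 to 0.7 and, for complications, an assumed 25% rate. The problem is thus modest for leakage and larger for overall complications. It is a worthwhile correction to the plan, not a flaw that undermines the study.

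A reader might also infer that clustering the standard errors would remove centre differences from the odds ratios. It would not: it corrects the stated uncertainty and leaves the estimates unchanged. A random intercept removes such confounding only in part when exposure is related to centre.

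**What to change.** Add one sentence to the Statistical Analysis section of the Protocol, for example: *The logistic models for leakage and for overall complications will use standard errors clustered on centre, with t-based critical values suited to the small number of centres; alternatively, they will include a random intercept for centre.* One of the two should be chosen before the data are analysed.

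This needs no new data, since the participating centres send the records to the coordinating centre, and it is a standard option in the named software. The cost is somewhat wider intervals for practice-related factors. Results for patient-level factors should hardly change.

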### **Sample size**

Considering that the ASA grade (I and II vs. III) is mostly significant among risk factors for anastomotic dehiscence [3, 5, 8], an estimation of the OR for anastomotic dehiscence and ASA grade is equal to 5.6 [20]; assuming a confidence interval for the estimation of the OR at 95% and a maximum error equal to 0.04, the required sample size is  $n=1,062$  (about 885 and 177 cases expected in ASA I-II and ASA III, respectively).

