**BACKGROUND**

Anastomotic leakage is a dreaded major complication after colorectal surgery [1]. The overall incidence of anastomotic dehiscence and subsequent leaks is 2 to 7 percent when performed by experienced surgeons [2-5]. The lowest leak rates are found with ileocolic anastomoses (1 to 3 percent) and the highest occur with coloanal anastomosis (10 to 20 percent) [6]. Leaks usually become apparent between five and seven days postoperatively. Almost half of all leaks occur after the patient has been discharged, and up to 12 percent occur after postoperative day 30 [4]. Late leaks often present insidiously with low-grade fever, prolonged ileus, and nonspecific symptoms attributable to other postoperative infectious complications. Small, contained leaks present later in the clinical course and may be difficult to distinguish from postoperative abscesses by radiologic imaging, making the diagnosis uncertain and underreported.

There is no uniform definition of an anastomotic dehiscence and leak [5]. In a review of 97 studies, as an example, 56 different definitions of an anastomotic leak were used [7]. The majority of reports define an anastomotic leak using clinical signs, radiographic findings, and intraoperative findings [8, 9]. The clinical signs include: Pain, Fever, Tachycardia, Peritonitis, Feculent drainage, Purulent drainage. The radiographic signs include: Fluid collections, Gas containing collections. The intraoperative findings include: Gross enteric spillage, Anastomotic disruption.

Risk factors for a dehiscence and leak are classified according to the site of the anastomosis (extraperitoneal or intraperitoneal). A prospective review of 1598 patients undergoing 1639 anastomotic procedures for benign or malignant colorectal disease found a significantly increased

risk of anastomotic leak with extraperitoneal compared with intraperitoneal anastomoses (6.6 versus 1.5 percent; 2.4 percent overall) [10].

Major risk factors for an extraperitoneal anastomotic leak include: The distance of the anastomosis from the anal verge (Patients with a low anterior resection and an anastomosis within 5 cm from the anal verge are the highest risk group for an anastomotic leak), Anastomotic ischemia, Male gender, Obesity.

Major risk factors for an intraperitoneal anastomotic leak include: American Society of Anesthesiologists (ASA) score Grade III to V, Emergent surgery, Prolonged operative time, Hand-sewn ileocolic anastomosis.

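### The sample size claims a maximum error of 0.04 on an odds ratio of 5.6, but 885 and 177 patients give an expected 95% CI of about 2.4–13.3 (2% leaks) to 3.4–9.1 (7% leaks)

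*Protocol*

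**What the plan says.** The Protocol's Sample size section takes ASA grade (I–II versus III) as the leading risk factor and states that "an estimation of the OR for anastomotic dehiscence and ASA grade is equal to 5.6". It then continues, "assuming a confidence interval for the estimation of the OR at 95% and a maximum error equal to 0.04", and concludes that 1,062 patients are required, with "about 885 and 177 cases expected in ASA I-II and ASA III, respectively". It gives no leak rate, formula, power or scale for the 0.04.

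The only incidence figures are in the Background. One is a general range: "The overall incidence of anastomotic dehiscence and subsequent leaks is 2 to 7 percent". The other is from a single review of extraperitoneal versus intraperitoneal anastomoses: "6.6 versus 1.5 percent; 2.4 percent overall".

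Under Statistical Analysis, "The odds ratio (OR) will be presented followed by its 95% confidence interval". Under Methods, "A total of more than 1,160 patients is expected based on a mean of 50 cases/year per center".

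**The concern.** The odds ratio is the only quantity that the sentence names as being estimated, so as written 0.04 is the maximum error on the odds ratio. The precision of an odds ratio is governed mainly by the number of events. At leak rates of 2 to 7%, 1,062 patients yield only about 21 to 74 leaks, split between two groups. That cannot fix an odds ratio of 5.6 to within a few hundredths.

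This sentence is the only justification given for the study's size. If it is wrong, 1,062 is presented as the number needed for a precision that it does not deliver. A reader would then expect a far sharper estimate of the ASA effect than the study can produce.

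**Working it through.** **Inputs.** Odds ratio 5.6, group sizes 885 and 177 (5:1), confidence level 95% (z = 1.96) and margin 0.04, all from Sample size. Overall leak rates of 2%, 2.4% and 7% come from the Background; 5% is added as an intermediate value.

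**Can 1,062 be reproduced as stated?** No. No formula for the precision of an odds ratio gives 1,062 from these inputs (see step 3).

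**Step 1: group risks.** For each overall leak rate p, find p0 (ASA I–II) and p1 (ASA III) such that

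- [p1/(1−p1)] / [p0/(1−p0)] = 5.6
- (885·p0 + 177·p1)/1,062 = p

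**Step 2: expected interval.** SE(log OR) = √(1/a + 1/b + 1/c + 1/d), where a to d are the expected cell counts. The 95% CI is 5.6 × exp(±1.96·SE).

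At 2%, for example, the expected cells are 10.30 leaks and 874.70 without in ASA I–II, and 10.94 and 166.06 in ASA III. SE = √(0.0971 + 0.0011 + 0.0914 + 0.0060) = 0.442, and 1.96 × 0.442 = 0.87.

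| Overall leak rate | Leaks | p0 / p1 | SE(log OR) | Log half-width | ÷ 0.04 | Expected 95% CI |
|---|---|---|---|---|---|---|
| 2% | 21 | 1.2% / 6.2% | 0.442 | 0.87 | 22 | 2.35–13.33 |
| 2.4% | 25 | 1.4% / 7.4% | 0.405 | 0.79 | 20 | 2.53–12.39 |
| 5% | 53 | 3.0% / 14.9% | 0.288 | 0.57 | 14 | 3.18–9.85 |
| 7% | 74 | 4.3% / 20.3% | 0.249 | 0.49 | 12 | 3.44–9.13 |

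**Step 3: patients needed for an error of 0.04**, at the same 5:1 split, for leak rates from 7% to 2%:

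- Log-OR scale, 1,062 × (1.96·SE/0.04)²: about 158,000 to 499,000.
- 4% relative precision, with |ln(1−0.04)| in place of 0.04: about 152,000 to 479,000.
- OR scale, 1,062 × (5.6·1.96·SE/0.04)²: about 5 to 16 million.

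**Step 4: does any leak rate rescue it?** Scanning overall rates from 0.5% to 95%, the SE is smallest at about 27%. The log half-width there is 0.34, the interval is 3.98–7.88, and about 77,000 patients would be needed on the log scale. The 1,160 patients expected under Methods, at the same split, give 2.4–12.8 (2%) to 3.5–8.9 (7%).

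**Step 5: what does 0.04 fit?** An absolute margin comes close at low leak rates only. The half-widths are 1.96·√[p1(1−p1)/177] for the ASA III leak proportion and 1.96·√[p0(1−p0)/885 + p1(1−p1)/177] for the risk difference.

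| Overall leak rate | ASA III proportion | Risk difference |
|---|---|---|
| 2% | 0.036 | 0.036 |
| 2.4% | 0.039 | 0.039 |
| 5% | 0.052 | 0.054 |
| 7% | 0.059 | 0.061 |

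Two routes lead to 1,062. One is a single proportion of 8% ± 4 points: 1.96² × 0.08 × 0.92/0.04² = 176.7, so 177, and 6 × 177 = 1,062. The other is a risk difference with half-width 0.04 at about 2.5% overall leakage. The Protocol states neither target. The 8% is an inference and appears nowhere in it.

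**Step 6: power.** For an odds ratio of 5.6 against 1, the Wald approximation gives 97.3% at 2%, 98.9% at 2.4% and above 99.9% at 5–7%. Simulated Fisher exact tests give about 95%, 97%, 99.9% and 100% at 2%, 2.4%, 5% and 7%.

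**The case against.** The strongest reply is that the sentence is ambiguous. The reference to the odds ratio qualifies the confidence interval, while 0.04 carries no scale of its own. The margin could be the absolute risk difference between the ASA groups: with the stated odds ratio, split and confidence level, its half-width is 0.039 at the 2.4% leak rate that the Background cites. On that view the sample size is sound and only the label is incomplete.

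This is plausible, and it is a better candidate than a single proportion that needs an unstated 8%. It does not rescue the text. The Sample size section mentions no risk difference, proportion or leak rate, and the odds ratio is the only estimand in the sentence. The risk-difference reading also fails in the upper part of the Protocol's own leak range (0.054 to 0.061 at 5–7%). That another quantity fits 0.04 supports the diagnosis of a misattached margin.

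A second reply is that nothing follows from the error. Most of this stands: no analysis uses 0.04, the odds ratio will be reported with its actual interval, the expected lower limit stays above 1 throughout 2–7%, and power is high. This limits the consequence but does not make the stated precision true.

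A third reply is that the formula may sit in a statistical analysis plan. That would excuse missing detail, but not a figure in the Protocol that its own inputs contradict.

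**Conclusion.** The concern holds. Read as an error on the odds ratio, 0.04 is not met on an absolute, relative or log scale at any leak rate. Within the Background's 2–7%, the expected log half-width is 12 to 22 times the stated margin, and the upper confidence limit is about 2.7 times (7%) to 5.7 times (2%) the lower.

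The exact intervals rest on the large-sample variance of the log odds ratio, the 885/177 split, a true odds ratio of 5.6 and the Background's leak rates. The conclusion does not depend on the leak rate, since even the most favourable one leaves a log half-width of 0.34.

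The error lies in the stated justification. It does not show that 1,062 patients are too few to detect an odds ratio of 5.6.

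**What to change.** Keep n = 1,062. In the Sample size section, remove 0.04 as the margin for the odds ratio and state the expected interval with its assumed leak rate. Suggested wording: *At an overall leak rate of 2.4%, 885 ASA I–II and 177 ASA III patients give an expected 95% CI of about 2.5–12.4 around an odds ratio of 5.6 (about 3.4–9.1 at 7%).*

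If 0.04 was meant as the margin for the ASA III leak proportion or for the risk difference between ASA groups, name that quantity, state the assumed leak proportions and give the formula. Note also that the margin widens to 0.05–0.06 at 5–7% overall leakage.

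The cost is the rewording of one sentence. No patients, data collection or analyses change; the stated precision becomes less favourable.

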Appendix 1 **DULK SCORE [14]**

	Valori Normali	Score	Valori alterati	Score
Febbre	$\leq 38.0^{\circ} \text{C}$	0	$\geq 38.0^{\circ} \text{C}$	1
Frequenza cardiaca	$\leq 100 \text{ bpm}$	0	$\geq 100 \text{ bpm}$	1
Frequenza respiratoria	$\leq 30 \text{ atti/min}$	0	$\geq 30 \text{ atti/min}$	1
Diuresi	$\geq 30 \text{ ml/h o } 700 \text{ ml/die}$	0	$\leq 30 \text{ ml/h o } 700 \text{ ml/die}$	1
Stato mentale	Normale stato mentale	0	Agitazione o Letargia	2
Condizioni cliniche	Stabili o in miglioramento	0	Deterioramento	2
Segni di ileo	No	0	Ileo	2
Ritenzione gastrica	No	0	Ritenzione Gastrica	2
Deiscenza della fascia	No	0	Deiscenza della fascia	2
Dolore addominale o altri non di ferita	No dolore	0	Dolore non della ferita	2
Segni di infezione	No aumento leucociti o PCR	0	Aumento dei leucociti di $\geq 5\%$ o della PCR	1
Funzionalità renale	No aumento Urea o Creatinina	0	Aumento di Urea o Creatinina di $\geq 5\%$	1
Stato nutrizionale	Dieta Normale	0	Enterale/Parenterale Totale	1/2
TOTALE				

